³⁴Department of Neurology, The Royal Children's Hospital, Murdoch Children's Research Institute and the University of Melbourne, Victoria, Australia.

³⁵French Centre for Paediatric Stroke, Hôpital Bellevue CHU Saint-Étienne, France

*Listed in Appendix 1

Corresponding author

[name]

[contact]

Running Title: PASTA Study Protocol

Key Words: Treatment, Pediatric Stroke, Focal Cerebral Arteriopathy, Steroid, Randomized Controlled Trial, FCA, Methylprednisolone, Protocol, PASTA

PASTA (Pediatric Arteriopathy Steroid Aspirin) trial

Pediatr Stroke. 2023;6: 21-42

www.pediatricstrokejournal.com

pediatric stroke

Study Protocol

Abstract

Rationale

Focal cerebral arteriopathy (FCA), a unilateral, monophasic disease of the intracranial arteries, is one of the most common etiologies of pediatric stroke. Imaging and laboratory evidence suggest an underlying inflammatory mechanism. The arteriopathy can progress over days to weeks, conferring a high risk of additional ischemic brain injury. Given its presumed inflammatory origin, there has been recently an emerging trend to intervene with corticosteroid treatment. However, there is a paucity of evidence on whether steroid treatment improves outcomes.

Aim

The aim of this study is to investigate whether high dose corticosteroids result in greater and faster improvement of focal stenosis in children with stroke and FCA and how this intervention influences neurological and neuropsychological outcomes as well as quality of life.

Sample size estimates

A sample size of 64 patients assigned 1:1 to the two study arms is required to detect a clinically relevant difference of 2.0 in the primary outcome with a power of 80% at a two-sided

PASTA (Pediatric Arteriopathy Steroid Aspirin) trial

Pediatr Stroke. 2023;6: 21-42

www.pediatricstrokejournal.com

pediatric stroke

Study Protocol

alpha-level of 0.05.

Methods and design

This is a Prospective Randomized Open, Blinded Endpoint (PROBE) study involving 27 centers in Europe and Australia. Patients between 6 months and 18 years with a unilateral arteriopathy will be enrolled during a recruitment period of 3 years. A total of 70 participants (accounting for 8% dropouts) will be centrally randomized to standard care (including aspirin) alone or standard care plus high-dose-corticosteroids (experimental arm) in a ratio 1:1.

Study outcomes

The primary outcome measure is change in Magnetic resonance imaging (MRI) based FCA Severity Score (FCASS) from baseline to 1 month, compared between the two study arms. In addition, the study comprises various clinical and imaging-based information as well as analyses of adverse reactions.

Discussion

This will be one of the first prospective treatment trials in the field of pediatric stroke. The preparation for the study has already impacted stroke care of children worldwide through development of international collaborative trial networks and standardized neuroimaging based vascular scoring system.

PASTA (Pediatric Arteriopathy Steroid Aspirin) trial

Pediatr Stroke. 2023;6: 21-42

www.pediatricstrokejournal.com

pediatric stroke

Study Protocol

PASTA (Pediatric Arteriopathy Steroid Aspirin) trial

Pediatr Stroke. 2023;6: 21-42

www.pediatricstrokejournal.com

Introduction and rationale

Due to the suspected inflammatory cause of focal arteriopathy of the inflammatory type (FCA-i), it is increasingly treated with steroids - so far without firm evidence.¹⁻⁴

In more than half of children with arterial ischemic stroke (AIS), arteriopathy is the underlying cause.⁵ This is further subdivided into a small vessel as well as a large vessel bilateral and unilateral arteriopathy depending on the distribution of the affected vessels. The term focal cerebral arteriopathy (FCA) is often used synonymously with the term unilateral arteriopathy in the literature. When the term is used in this sense, no distinction is made as to what is the cause of this arteriopathy.⁶

In addition, the term FCA is used much more specifically for a subtype of unilateral arteriopathy^{5,7}: This is a mostly unilateral monophasic disease of the cerebral arteries. Although the exact pathophysiology for the latter remains unknown, there is increasing evidence of a transmural inflammatory process of the vessel wall (see Fig. 1).⁸⁻¹⁰ This has led to the additional designation of the term "FCA of the inflammatory type" (FCA-i).⁹ Which distinguishes this from other forms of unilateral arteriopathy, such as moyamoya and dissection. The question of the extent to which FCA-i can also be present bilaterally is the subject of current research.

According to a retrospective Australian-Swiss study, steroid treatment in FCA-i is associated with

PASTA (Pediatric Arteriopathy Steroid Aspirin) trial

pediatric stroke

Study Protocol

a significantly better neurologic outcome¹ and an uncontrolled case series, showed that steroid treatment reduced vessel wall enhancement.¹⁰ In contrast, it has also been postulated that infectious mechanisms may play a role in the pathophysiology of FCA-i, and concerns have been raised about possible adverse effects of steroid treatment on these mechanisms.^{11,12} The mechanism has best been studied for varicella related FCA-i: After systematic infection varicella virus remains in ganglions (“sleeping”). By reactivation there is a neuronal transport of the virus, followed by inflammatory process in the vessel wall.¹³ For other disease-causing microorganisms, the pathophysiology is less clear, but likely similar. Reflective of the resulting uncertainty and equipoise, a Delphi survey of pediatric stroke specialists identified a steroid trial in children with FCA-i as the most important and feasible trial in this research field.⁴

To assess the severity of stenosis and the course of FCA-i in a standardized manner, the Focal Cerebral Arteriopathy Severity Score (FCASS) was developed in 2018. It is calculated based on the degree of arterial stenosis in MR, CT or conventional angiography in five cerebral arterial segments. Consistent with the natural history of FCA-i, FCASS increases in the first months of the disease and then decreases thereafter. The score was shown to be reliable and to correlate with long-term outcome as well as stroke volume.^{12,14}

The objectives of this study are to evaluate if early anti-inflammatory treatment may influence

PASTA (Pediatric Arteriopathy Steroid Aspirin) trial

pediatric stroke

Study Protocol

the course of arteriopathy, improve clinical outcomes, and prevent stroke recurrence in children with FCA-i.

The primary hypothesis is, that children with FCA-i treated with a course of high dose methylprednisolone/prednisolone will show greater improvement of focal stenosis and arteriopathy as measured by FCASS.

Methods

Design

This is a PROBE-study, comparing a high-dose course of intravenous methylprednisolone/oral prednisolone plus standard care versus standard care alone in children with FCA-i. The study will be conducted in 27 centers in Australia, Austria, France, Germany, Switzerland, and the United Kingdom.

Recruitment of participants is planned to occur over a period of 36 months. The data collection is shown in Fig. 2.

At the time of this publication the study protocol was approved by all corresponding regulatory authorities and the local ethic committees in Switzerland (BASEC-ID: 2021-00453), Austria (EK Nr: 2136/2021), France (N° de dossier: 21.04056.000061–22014), Germany (Aktenzeichen:

PASTA (Pediatric Arteriopathy Steroid Aspirin) trial

pediatric stroke

Study Protocol

2022-066-f-A) as well as UK (IRAS ID: 305395) and Australia (RCH HREC Reference Number: 78937). The study is registered at ClinicalTrials.gov (NCT04873583).

Patient population

All patients older than 6 months and younger than 18 years with unilateral FCA-i will be screened on admission. The complete eligibility criteria are provided in table 1.

Inclusion criteria	Exclusion criteria
1. Written informed consent (legal representative)	1. Previous stroke
2. Age 6 months to under 18 years	2. Genetic vasculopathies include ACTA2, neurofibromatosis type 1, trisomy 21
3. Randomization possible within 48 hours of diagnosis and maximum 96 hours after symptom onset	3. Moyamoya or sickle cell disease
4. Symptomatic unilateral cerebral arteriopathy (newly acquired neurological deficits of proven ischemia and unilateral stenosis/vessel irregularity on neuroimaging)	4. Craniocervical arterial dissection
5. Female participants age \geq 13: Negative pregnancy test	5. Primary (small vessel) and secondary angiitis of the CNS
	6. Bilateral arteriopathy
	7. Underlying systemic disorders e.g., rheumatological
	8. On steroid treatment at disease onset
	9. Contraindication to corticosteroid treatment
	10. Inability to follow study-procedures
	11. Participation in another interventional study

Table 1: Eligibility criteria

PASTA (Pediatric Arteriopathy Steroid Aspirin) trial

pediatric stroke

Study Protocol

The diagnosis of unilateral cerebral arteriopathy (inclusion criterion 4) will be made on site by the respective study team. If the diagnosis is not clear, the sponsor will be contacted to review the MRI images together with the neuroradiologists at the sponsor's site. Subsequently, the sponsor and study site will seek a joint agreement as to whether or not the patient fulfills the eligibility criteria.

Randomization and blinding

Allocation will be done in a 1:1 ratio of standard care alone (including aspirin) or standard care plus corticosteroids (See Fig. 3) using web-based randomization with secuTrial.

Probabilistic minimization will be used, accounting for the following stratification factors: age (6 months through 5 years, 6 years through 11 years, 12 years to under 18 years) and pediatric National Institute of Health Stroke Scale (Ped-NIHSS; < 7, 7 to 12, >12).

Trial participants and local data collectors will not be blinded, as steroid treatment causes obvious clinical signs and symptoms. Imaging outcomes will be centrally assessed by blinded neuroradiologists.

The telephone-interview-based assessments of RRQ (Recurrence and Recovery Questionnaire), mRS (modified Rankin Scale) and VABS (Vineland Adaptive Behavior Scales) will be performed

PASTA (Pediatric Arteriopathy Steroid Aspirin) trial

pediatric stroke

Study Protocol

blinded centrally for all study participants.

Intervention

Participants in both study arms will be treated based on standard care, including antithrombotic treatment with daily oral aspirin (3-5mg/kg/day, maximum 150mg/day). The hyperacute treatment (including intravenous thrombolysis and endovascular thrombectomy) may be performed according to local protocol. Start with any type of anticoagulation is possible and should be done as by local protocol. Switch or start of aspirin is mandatory at latest at inclusion. Suggestions (see supplementary) for standard care are given to the sites but noncompliance is not a deviation to the protocol. These suggestions have been discussed and approved by the international steering committee of the PASTA trial (see Appendix 1).

In addition, participants in the treatment arm will receive 3 days of intravenous methylprednisolone 30mg/kg/day (max. 1000mg/dose) in one daily dose. This is followed by therapy with oral prednisolone 1 mg/kg/day (max. 40mg/day) for 2 weeks and 0.5mg/kg/day (max. 20mg/day) for another 2 weeks.

Outcomes

The Primary Outcome is the change in FCASS from baseline examination to 1 month. In

PASTA (Pediatric Arteriopathy Steroid Aspirin) trial

Pediatr Stroke. 2023;6: 21-42

www.pediatricstrokejournal.com

addition, various imaging data, clinical and safety outcomes will be assessed (see table 2).

Primary Outcome

● Change in FCASS from baseline to 1 month
Secondary Outcomes
Imaging

● Change in FCASS from baseline to 6 months● Volume of stroke (in FLAIR and DWI-sequences) at baseline, 1, 3 and 6 months by modified pediatric ASPECTS● Residual arteriopathy at 6 months by FCASS
Clinical

● Functional impairment outcome by PSOM at 1, 3, 6 and 12 months● Recovery by RRQ at 1, 3, 6, and 12 months● Degree of disability or dependence by mRS at 1, 3, 6, and 12 months● Adaptive function by VABS at 6 and 12 months● For children aged >2 years, quality of life at 12 months, by PSQLM● Neurocognitive outcome at 12 months
Mixed clinical/imaging

● Stroke recurrence assessed at 1, 6 and 12 months defined as:
- New focal neurological deficit(s) or- Worsening of the neurological deficits by > 4 pedNIHSS points lasting for more than 24 hours with new or increased diffusion restriction in the corresponding vascular territory, or- New areas of clinically silent infarction, remote from the initial infarct
Safety Outcomes

● Late diagnosis of progressive large to medium vessel childhood primary angiitis of the CNS● Adverse events (abnormal blood pressure, abnormal blood glucose, behavioral problems, infections, gastrointestinal irritation, electrolyte abnormalities requiring

PASTA (Pediatric Arteriopathy Steroid Aspirin) trial

intervention or weight gain)

- Infectious episodes requiring hospitalization
- Serious adverse events related to the study intervention requiring medical intervention

Table 2: Outcome Measures. FCASS: Focal cerebral arteriopathy severity score; ASPECTS: Alberta stroke program early CT score, PSOM: Pediatric Stroke Outcome Measure; RRQ: Recurrence and Recovery Questionnaire; mRS: modified Rankin Scale; VABS: Vineland Adaptive Behavior Scale; PSQLM: Pediatric Stroke Quality of Life Measure; ped NIHSS: pediatric National Institute of Health Stroke Scale.

Imaging Outcomes

Magnetic resonance imaging and angiography (MRI/MRA) will be performed at baseline, 1 and 6 months and, if clinically indicated at 3 months. The imaging protocol will comprise at least DWI/ADC, FLAIR, T2-weighted, time of flight (ToF) MR angiography and SWI sequences. At baseline neck vessel and vessel wall imaging should be considered. MRIs should be performed at 3 Tesla and without sedation or anesthesia if possible. All images will be assessed centrally by two independent neuroradiologists.

The degree of arterial stenosis at different time points is measured using FCASS in MRA.

Stroke Volume is measured by modified pediatric ASPECTS, a semi quantitative imaging score in childhood stroke where each abnormal area is assigned one point. Higher scores represent greater volumes, with a maximum possible score of 30 (15 per hemisphere).^{15,16}

Clinical Outcomes

PASTA (Pediatric Arteriopathy Steroid Aspirin) trial

pediatric stroke

Study Protocol

The pedNIHSS, an adaptation of the adult NIHSS to the pediatric population, is used to assess the severity of stroke.¹⁷ The Pediatric Stroke Outcome Measure (PSOM), which is used to determine neurologic outcome, was developed, and validated specifically for pediatric stroke. It addresses pediatric specific domains such as development, behavior and cognition in addition to sensory-motor and language function.^{18,19} To improve quality of data for pedNIHSS and PSOM, explanatory videos were created for all investigators. These are available at (<https://www.pasta-trial.ch>).

By telephone, the modified Rankin Scale (mRS) is collected to determine disability or dependence and the Recurrence and Recovery Questionnaire (RRQ) to determine recovery and recurrence. In addition, the Vineland adaptive behavior scale (VABS) is collected to monitor behavior and cognitive abilities. The VABS and mRS are widely used tests, which are well validated.^{20,21} The RRQ was specifically developed and validated for pediatric stroke patients and addresses pediatric- specific problems of manifestation of stroke and also difficulties in reliable clinical examination.²²

At the end of follow-up, Quality of life is assessed using the Pediatric Stroke Quality of Life Measure (PSQLM)²³ and standardized neurocognitive testing (using either WISC-V or WPPSI-IV, depending on age) is performed. Within the framework of this examination, children over the

PASTA (Pediatric Arteriopathy Steroid Aspirin) trial

pediatric stroke

Study Protocol

age of 8 are additionally assessed for executive functions using subtests of the Delis-Kaplan Executive Function System (D-KEFS) and attention using Continuous performance task (CPT-III).

Data monitoring body

On site monitoring will be conducted at the first 5 sites that enroll a participant as soon as their first participant has reached the 30-day follow-up visit. Subsequent on-site and remote monitoring visits will be done randomly and by risk-based assessment.

Central data monitoring and validation will be performed according to a separate monitoring plan continuously for each site. This will include regular verification of the completeness, accuracy, and plausibility of the entered data and to query the site and follow up anything requiring clarification. No interim analyses are planned and no safety stopping points are defined.

Sample size estimates

For 13 patients of a retrospective study the standard deviation of the change in FCASS from baseline to maximum severity of arteriopathy was 2.8.¹⁴ Based on this standard deviation and a two-sample means test, 64 patients (32 in each group) are required to detect a difference of 2.0 with a power of 80% at a two-sided alpha-level of 0.05.

PASTA (Pediatric Arteriopathy Steroid Aspirin) trial

pediatric stroke

Study Protocol

To account for dropouts (8%), we will enlarge the sample size to 70 patients (35 in each group).

Statistical Analyses

The primary analysis will follow the intention-to-treat (ITT) principle. The primary outcome and secondary continuous variable outcomes that are measured multiple times during follow-up will be assessed in a repeated-measure, mixed-effects linear model.

Neurocognitive outcomes measured at 1 year will be analyzed using a mixed-effects linear model, binary outcomes (recovery, residual arteriopathy) will be assessed using generalized linear mixed-effects models, Time-to-event outcomes (stroke recurrence, infection requiring hospitalization, progressive arteriopathy) will be analyzed using Cox-regression, accounting for the stratification factors used at randomization (country and baseline FCASS).

We will perform a subgroup analysis according to baseline FCASS (<8 vs ≥8), accompanied by an appropriate test of interaction. Moreover, we will test whether the baseline FCASS (used continuously) has an influence on the association between steroid treatment and modified ASPECT score, i.e. whether there is effect modification (interaction).

Scores measured repeatedly over time (FCASS, mRS, PSOM, VABS, modified pediatric ASPECT) might be considered as categories. Patients may shift from category to category several times

PASTA (Pediatric Arteriopathy Steroid Aspirin) trial

pediatric stroke

Study Protocol

over the duration of follow-up. We will additionally use mixed effects ordered logistic regression analysis on this data (shift analysis). Moreover, we will perform subgroup analysis according to country and baseline FCASS (<8 vs ≥8).

Discussion

Treatment of pediatric stroke is limited to secondary prevention in the vast majority of cases.²⁴⁻²⁶ In contrast, treatment of FCA-i with steroids would be a therapy that directly intervenes in the acute course of the disease. There is much experience with the steroid dosing regimen, which is consistent with standard practice for other immunotherapy treatment protocols in children.^{27,28} But there is no evidence for this treatment in FCA-i. Despite this lack of evidence, a recent review (meta-analysis) on immunotherapy in pediatric stroke has shown that 80% of children with FCA-i were treated with corticosteroids.² For this reason, and because of the fact that FCA-i is at high risk for stroke recurrence, the project that we present here has been identified as the most important pediatric trial for the treatment of AIS.^{4,29} Aside from the trials of stroke prevention in sickle-cell disease³⁰, this is one of the first randomized, controlled treatment trials in pediatric AIS. In addition, the PASTA study is generating one of the largest prospective cohorts of patients with FCA-i. This will make it possible to systematically study FCA-i in an unprecedented way and to obtain a better insight into the pathophysiology of FCA-i.

PASTA (Pediatric Arteriopathy Steroid Aspirin) trial

Pediatr Stroke. 2023;6: 21-42

www.pediatricstrokejournal.com

pediatric stroke

Study Protocol

Nevertheless, the study has some limitations. The diagnosis of FCA-i remains challenging in the acute setting for the following reasons: According to the traditional definition, the disease is monophasic - this cannot be detected in the acute situation. Imaging findings often overlap with intracranial dissection, so that differentiation is often difficult. Moyamoya is differentiated from FCA-i by the presence of collateral vessels. However, these may be absent in early stage moyamoya.³¹ Biomarkers such as varicella serology in CSF are only effective in certain cases.³² In recent years, vessel wall imaging has been increasingly used as a diagnostic biomarker.³³ However, vascular wall imaging with contrast enhancement cannot be performed within a study setting for ethical reasons. Overall, the diagnosis is therefore still often based on expert opinion by experienced stroke specialists. Accordingly, the inclusion criteria for this study were defined more broadly - so that the presence of unilateral arteriopathy after exclusion of any differential diagnoses is sufficient. As a support the centers will be guided in diagnosis by the sponsor team and their neuroradiologists experienced in this diagnosis.

As FCA-i is a rare disease, the number of cases in each center included in the study is very low. This means that the experience of the investigators of the individual centers in handling the study will be low and stratification by center is not possible. This and the lack of complete blinding of the investigators increases the risk of observer bias. Since the imaging outcomes and

PASTA (Pediatric Arteriopathy Steroid Aspirin) trial

Pediatr Stroke. 2023;6: 21-42

www.pediatricstrokejournal.com

thus the primary outcome are collected centrally, they are not affected by this risk. To reduce risk in recording clinical outcomes, investigators were provided with videos for learning the ped-NIHSS and PSOM in a standardized manner. In addition, the collection of various clinical outcomes is done centrally via telephone interview by a blinded investigator. As a further limitation, it should be mentioned that a surrogate marker was chosen as the primary outcome here. However, it could be shown that this correlates with the clinical outcome and that this has a high reliability.^{12,14} In addition, to validate the results of the primary outcome, various clinical outcomes will also be assessed in the PASTA study.

Summary and conclusion

This prospective, parallel group, two-arm, randomized controlled, open-label clinical trial with blinded assessment of outcome will show if high-dose steroid treatment in addition to standard care is better than standard care alone in patients with FCA-i.

Trial status

This is protocol version 5, dated August 22, 2022, Site initiation started on November 2021. To date 7 participants have been randomized.

PASTA (Pediatric Arteriopathy Steroid Aspirin) trial

Funding

This trial is financed by the Swiss National Science Foundation via the “Investigator-initiated clinical trials – IICT” grant # 33IC30 193039

Authors’ Contributions/Conflicts of Interest Statement

MS, HF, MM, FO and SB designed the study, MS, AD, EP, JF and SB obtained funding. MS, PM, LS, and MB wrote the study protocol. DB wrote this publication. MS, LS, MSa, RM, GO, DB are involved in the set-up of the study, data collection, analysis, and interpretation of the data. EP is the expert in charge of the organization of the MRI. All Steering Committee members mentioned as authors and all Principal investigators have read the protocol, given input and accepted it with a signature. All authors read, edited, and approved the final manuscript. The Authors declare that there is no conflict of interest

References

PASTA (Pediatric Arteriopathy Steroid Aspirin) trial

pediatric stroke

Study Protocol

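### The steroid exclusion stops at disease onset and leaves open the interval up to randomization (as long as 96 hours), so a child already started on steroids can be randomized to, and analysed in, the control arm

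*Protocol*

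**What the plan says.** Under Patient population, the Protocol states that "The complete eligibility criteria are provided in table 1", so the table can be read as the whole list. Exclusion 8 is the only criterion about prior steroid use: "On steroid treatment at disease onset". Inclusion criterion 3 sets the time limit for entry: "Randomization possible within 48 hours of diagnosis and maximum 96 hours after symptom onset".

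The Design section describes the trial as "comparing a high-dose course of intravenous methylprednisolone/oral prednisolone plus standard care versus standard care alone in children with FCA-i". The Intervention section does not mention steroids given before randomization. It says that hyperacute treatment "may be performed according to local protocol", and that suggestions "for standard care are given to the sites but noncompliance is not a deviation to the protocol".

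On background use, the Introduction says that steroid treatment of this condition is growing without firm evidence. The Discussion cites a review in which "80% of children with FCA-i were treated with corticosteroids".

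Under Statistical Analyses, the primary analysis is by intention to treat. Under Sample size estimates, 32 per arm is derived from a difference of 2.0 and an SD of 2.8, and then: "To account for dropouts (8%), we will enlarge the sample size to 70 patients".

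**The concern.** The two criteria use different time anchors. The steroid exclusion looks at one moment, disease onset. The entry window runs for up to 96 hours after symptom onset. Between the two, a treating team that suspects inflammatory arteriopathy could start the drug class under test, and the child would still be eligible. The other exclusions, such as a contraindication to corticosteroids, inability to follow procedures or participation in another trial, do not catch this child.

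What is at stake is the contrast. A control child who has had steroids is not a clean example of standard care alone, yet intention-to-treat rightly keeps that child in the control arm. If steroids improve the FCASS, the control mean moves toward the steroid mean and the estimated difference shrinks. No analysis plan can restore contrast lost in this way. Because the exposure comes before allocation, eligibility can remove it without touching the intention-to-treat principle, whereas dropping such children after randomization would breach it.

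**Working it through.** **1. Does any criterion cover the gap?** Take a child off steroids at onset, started on them on day 2 and randomized on day 3, within 48 hours of diagnosis.
- Inclusion 3: met.
- Exclusion 8: not triggered, because the child was not on steroids at onset.
- Exclusions 1 to 7 concern previous stroke or other diagnoses. Exclusions 9 to 11 concern contraindication, study procedures and other trials. None is triggered by the steroid start.

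As written, the child is eligible.

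**2. Reproducing the plan's own figures.** Inputs from Sample size estimates: difference 2.0, SD 2.8, two-sided alpha 0.05, power 80%, 1:1 allocation.
- Noncentrality at n per arm: difference / (SD × √(2/n)). At n = 32: 2.0 / (2.8 × √(2/32)) = 2.0 / 0.70 = 2.857.
- With 62 degrees of freedom the critical t is 1.999, and power from the noncentral t distribution is 80.3%. At 31 per arm it is 79.0%, so 32 is the smallest sufficient number: 64 in total.
- Dropout: 64 / 0.92 = 69.6, rounded up to 70.

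Both stated figures reproduce. The margin above 80% is 0.3 points.

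**3. Dilution.** Two quantities are needed, and the Protocol gives neither; both are assumptions.
- f = share of control children given steroids before randomization.
- s = share of the full-course effect that this exposure delivers.

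Effective difference = 2.0 × (1 − f × s), with the SD held at 2.8 and 32 per arm. For f = 20% and s = 0.5: 2.0 × (1 − 0.10) = 1.8; noncentrality 1.8 / 0.70 = 2.571; power 71.6%.

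| Share of effect (s) | f = 10% | f = 20% | f = 30% |
|---|---|---|---|
| 0.25 | 1.95, 78.3% | 1.90, 76.2% | 1.85, 73.9% |
| 0.5 | 1.90, 76.2% | 1.80, 71.6% | 1.70, 66.7% |
| 1 (bound) | 1.80, 71.6% | 1.60, 61.4% | 1.40, 50.4% |

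Each cell shows the effective difference and the power.

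**4. How plausible is s = 1?** The experimental course in the Intervention section is 3 days intravenous plus 2 weeks plus 2 weeks oral: 3 + 14 + 14 = 31 days. The entry window is at most 96 hours (4 days) from symptom onset and 48 hours (2 days) from diagnosis. Exposure confined to the time before randomization therefore covers at most 4 of 31 days, and about 2 if steroids follow the diagnosis. Time share is not effect share, so this does not fix s, but it makes s = 1 a bound and not an expectation.

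**5. Does exclusion help?** Suppose a share f of children in both arms is excluded and not replaced, leaving 32 × (1 − f) per arm: 28.8, 25.6 and 22.4 for f = 10%, 20% and 30%. Power at the full difference of 2.0 is then 75.9%, 70.7% and 64.7%. Keeping the children at s = 0.5 gives 76.2%, 71.6% and 66.7%, which is slightly better. Without replacement, exclusion gains power only if s is above about one half. If excluded children are replaced, so that enrolment still reaches 70 and 32 per arm are evaluable, power returns to 80.3%.

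**The case against.** The strongest case against is that the gap may rarely be used. Children are screened on admission, the study team makes the diagnosis on site, and the sites joined a trial founded on equipoise. Nothing in the Protocol shows a site starting steroids and then randomizing to a steroid-free arm. This stands as a limit on likelihood; it does not close the gap in the text.

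A reader might infer four stronger things, and the Protocol does not support them.
- **That power drops to 61% or 50%.** Those figures need the effect of a 31-day course from at most 4 days of exposure. A control child could receive the rest only by continuing steroids after randomization, which is a separate matter.
- **That most children would arrive pre-treated,** because the Discussion reports that "80% of children with FCA-i were treated with corticosteroids". That figure carries no timing and does not describe the trial sites. It shows that steroid use is common, not that it begins before allocation.
- **That the baseline FCASS is already a post-steroid value.** Inclusion 4 requires neuroimaging evidence of stenosis or irregularity before entry, and nothing says that the baseline scan follows a dose.
- **That the sample size is wrong.** It reproduces exactly, and a sample size statement need not list hypothetical contamination rates.

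Two further objections stand in part. Exclusion without replacement can cost more power than it saves (step 5 of the working), so the remedy depends on recruiting to the fixed target. The standard-care supplement and the case report form are not shown, so it cannot be said that prior steroid exposure goes unrecorded.

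**Conclusion.** The point holds as an eligibility gap with a conditional cost. Exclusion 8 does not reach steroids started between symptom onset and randomization, inclusion 3 allows up to 96 hours for this, and nothing else in the Protocol prevents such a child from being randomized to control. If steroids work, any such child biases the intention-to-treat difference toward zero.

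The size is unknown. Under the assumptions of a quarter to a half of the full effect and 10% to 20% of controls exposed, power falls from 80.3% to between 78.3% and 71.6%. With no exposed children there is no loss. These are illustrations that hold the SD at 2.8 and the true difference at 2.0; they are not estimates. Severity is minor to moderate: the wording should be closed because doing so is cheap, not because the trial is shown to be underpowered.

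**What to change.** - **Table 1.** Reconcile exclusion 8 with inclusion 3 so that the steroid exclusion runs from disease onset up to randomization. Children already started on steroids for this event are then not randomized. Use one term for onset in both criteria, since disease onset and symptom onset are not defined against each other.
- **Recruitment.** Continue to the planned 70, so that excluded children are replaced.
- **Children already enrolled.** Record steroid exposure before randomization as yes or no, if the case report form does not already do so. They stay in the intention-to-treat analysis.
- **Sample size statement.** Leave it unchanged.

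The cost is one line in Table 1 by amendment and at most one data item. Some otherwise eligible children in a rare disease are lost, and recruitment may take slightly longer. Trial status gives 7 participants randomized at the time of writing, so an amendment then would have covered the remaining 63 of 70. If sites already apply the exclusion up to randomization, the rewording loses no children and makes the 27 centres consistent.
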